7.0 Clinical Trials of Miglustat for Gangliosidoses and Relevant Clinical Studies

Miglustat is a small molecule that has partial bioavailability to the CNS after oral administration, and which reduces production of a number of glycosphingolipids, including GM1 and GM2 gangliosides, through inhibition of glucosylceramide synthase in the glycosphingolipid pathway, and may be useful to decrease the pathological accumulation of GM1 and GM2 gangliosides.⁷ Miglustat is approved in the United States, Europe, Canada, Switzerland, Turkey, Brazil, and Australia for treatment of adult Gaucher disease type I. Miglustat is approved in Europe, Canada, Switzerland, Turkey, Brazil, and Australia for treatment of Niemann-Pick disease type C.^{7,26}

Studies of miglustat in infantile, juvenile and adult gangliosidoses have demonstrated safety, but do not show significant clinical improvement.²³⁻²⁵ A study of miglustat therapy in two patients with infantile Tay-Sachs disease who were given miglustat for 12 months showed no adverse effects at a dose of 100 mg daily for 3 months (divided into 3 doses daily).²³ The dose was doubled, increased to 200 mg daily after 3 months (divided into 3 doses daily) and this resulted in diarrhea and weight loss.²³ Reducing the dose back to 100 mg daily resulted in resolution of the diarrhea and weight loss.²³ The patients were continued at this lower dose during the remainder of the 12 months of the study.²³ Notably, neither patient developed macrocephaly during the 12 months of treatment.²³ Concentrations of miglustat in the cerebrospinal fluid (CSF) versus plasma varied from 1.84% to 27.3% of the concentration in the plasma.²³ Although miglustat therapy was well tolerated at 100 mg daily, the patient's neurological symptoms continued to worsen and encephalic imaging studies showed worsening myelination patterns and brain atrophy.²³

In a 3-month safety and pharmacokinetic study of 11 pediatric GM2 gangliosidosis patients (5 with infantile and with 2 juvenile Tay-Sachs disease, 1 with infantile Sandhoff disease and 3 with juvenile Sandhoff disease), miglustat was dosed at 30-200 mg 3 times daily.²⁴ Patients with a body surface area (BSA) less than 0.8 m² were given miglustat 50-90 mg 3 times daily.²⁴

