A pharmacokinetic profile study of miglustat in healthy rats showed miglustat to be well absorbed after a single oral administration with an oral bioavailability of 40-60%. Miglustat is eliminated renally by glomerular filtration and active secretion. Hepatic clearance of miglustat was shown to be negligible. Miglustat was found to have good partitioning into most tissues evaluated, including bone marrow, lungs, heart, kidney, bladder, liver, stomach, and small and large intestine. Miglustat showed appreciable distribution into the rat brain tissue. The ratio of tissue:plasma AUC for the rat brain was 0.40. Miglustat elimination half-life in the rat plasma was approximately 5 hours, but was significantly longer in the brain tissue at 17 hours.²⁰

10.6 Miglustat elimination. The major elimination route for miglustat is renal. Miglustat is excreted unchanged in the urine.²⁶

10.7 Renal insufficiency. In adult Gaucher disease patients, initial starting dose may be reduced to 100 mg twice daily for creatinine clearance 50-70 ml/min/1.73 m²; 100 mg once daily for 30-50 ml/min/1.73 m²; and miglustat is not recommended for Gaucher patients with renal clearance less than 30 ml/min/1.73 m².²⁶

10.8 Hepatic disease. Miglustat is not metabolized and no dose adjustments are needed for hepatic function impairment.²⁶

10.9 Toxicology. The most common adverse effects of miglustat in adult Gaucher disease type I are gastrointestinal side effects of diarrhea (up to 100% of patients), flatulence (29-50% of patients), weight loss (39-67% of patients), abdominal pain (18-67% of patients), and benign intentional tremor (up to 33% of adult Gaucher disease type I patients).²⁵ The gastrointestinal side effects are due to miglustat's inhibition of the action of disaccharidase digestive enzymes in the gut, primarily maltase, sucrose, and to a lesser degree, lactase. The disaccharidase inhibition can cause side effects of osmotic diarrhea when patients eat dairy foods, starchy foods such as bread, pasta and potatoes, and foods containing a high amount of sugar.^{26,27} Overdoses in adults lead to neutropenia, which predisposes to severe infection.

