There is limited human experience in the use of miglustat in children (especially those less than 4 years of age); as well as known risks of peripheral neuropathy, diarrhea and weight loss. Thrombocytopenia is a known side effect, so prior to surgery or invasive procedures, the child will require a CBC to ensure that the procedure can be safely performed.

Miglustat is in pregnancy risk category C in the USA. There are no adequate, well controlled studies of miglustat in pregnant women. In female rats given miglustat at doses of 20,60,180 mg/kg/day beginning 14 days before mating and continuing through day 17 gestation, decreased live births, decreased birth weight and complete litter loss was observed in the mid- to high-dose groups.²⁶ In the pregnant rats in the mid- to high-dose groups, delayed parturition and dystocia were also observed.²⁶

10.10 Dosing guidelines. Subjects with body surface area (BSA) < 0.73 m² will receive the goal dose of 100 mg miglustat three times daily, or the maximum dose tolerated up to 100 mg miglustat three times daily.

Rationale: studies of miglustat in infants and young children with gangliosidosis diseases have shown safety and tolerability. (References: (1) Maegawa GH, van Giersbergen PL, Yang S, Banwell B, Morgan CP, Dingemans J, Tiffet CJ, Clarke JT. Pharmacokinetics, safety and tolerability of miglustat in the treatment of pediatric patients with GM2 gangliosidosis. *Mol Genet Metab.* 2009 Aug;97(4):284-291; (2) Bembi B, Marchetti F, Guerci VI, Ciana G, Addobbati R, Grasso D, Barone R, Cariati R, Fernandez-Guillen L, Butters T, Pittis MG. Substrate reduction therapy in the infantile form of Tay-Sachs disease. *Neurology.* 2006 Jan 24;66(2):278-280; (3) Maegawa GH, Banwell BL, Blaser S, Sorge G, Toplak M, Ackerley C, Hawkins C, Hayes J, Clarke JT. Substrate reduction therapy in juvenile GM2 gangliosidosis. *Mol Genet Metab.* 2009 Sep-Oct;98(1-2):215-224.)

The safety, tolerability and pharmacokinetic study cited above (by Maegawa et al. 2009) showed safety and tolerability of miglustat in eleven children with GM2 gangliosidosis. In this study six of the patients had infantile phenotype (with ages ranging between 1 year and 5 years and BSAs ranging between 0.4 m² and 0.7 m²), and five patients had the juvenile phenotype (with ages ranging between 10.1 years and 20 years and BSAs ranging between 0.8 m² and 1.8 m²).

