The dosing of miglustat in the Maegawa study was described as follows: "In order to achieve adequate levels of miglustat in the central nervous system, the highest doses already examined in LSDs [lysosomal storage diseases] were chosen. The drug was administered at a maximum dose of 600 mg/day, divided into three doses. As the study was performed in a pediatric population, the dose was adjusted to the body surface area (BSA) of each patient." Children with BSA < 0.8 m² received miglustat dosed at 50 mg-90 mg 3 times daily, titrated to the maximum tolerated dose (up to 270 mg per day). The major dose-limiting drug-related adverse events that resulted in dose reductions of miglustat in Maegawa's study were gastrointestinal side effects secondary to miglustat's inhibition of disaccharidases in the gut, resulting in intolerance of dietary carbohydrates. For patients with BSA < 0.8 m², final doses, after titrating to maximum tolerated dose, ranged widely from 360 mg/m² to 450 mg/m², and the milligrams administered per day ranged from 15 mg/kg/day to 20.9 mg/kg/day.

Subjects with BSA 0.8 – 1.3 m² will receive the goal dose of 100 mg miglustat three times daily, or the maximum dose tolerated up to 100 mg miglustat three times daily.

Rationale: In Maegawa's 2009 study, patients with BSA within 0.8 m² to 1.3 m² received 100 mg 3 times daily.

Subjects with BSA > 1.3 m² will receive the maximum dose tolerated, up to 200 mg miglustat three times daily.

Rationale: In Maegawa's 2009 study, patients with BSA > 1.3 m² received 600 mg per day (200 mg 3 times daily), or the maximum tolerated dose, up to 200 mg 3 times daily.

10.11 Use of miglustat in this study. Before starting miglustat, patients will be initiated on the ketogenic diet, with goal of achieving a 4:1 ratio, and showing stability on the ketogenic diet for 2 weeks before starting miglustat therapy.

Miglustat dose will be prepared by dissolving contents of one 100 mg capsule in 10 ml of water. Only one dose of miglustat will be prepared at a time and the preparation must be used immediately and not stored for future use. Any unused solution during the initial dose escalation should be discarded. Miglustat dose will be prepared by patient's caregiver and caregiver will be counseled on pregnancy category C status and sperm parameter studies of miglustat. Caregiver should use a mask and gloves during preparation of miglustat solution.

The following written instructions will be given to the parents:

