The miglustat dose will be prepared by dissolving contents of one 100 mg capsule in 10 ml of water in a medication dosing syringe. The child's parents will be taught by the study investigator how to measure the 10 ml of water and mix with miglustat powder in the syringe prior to administration. Only one dose of miglustat will be prepared at a time and the preparation must be used immediately and not stored for future use. Any unused solution during the initial dose escalation should be discarded. Parent should use a mask and gloves during preparation of miglustat solution.

10.12 Miglustat dose titration schedule.

For subjects with a BSA of < 1.3 m², the goal dose will be 100 mg three times daily.

The miglustat dose will be titrated over approximately 8 weeks to a goal dose of 100 mg 3 times daily in pediatric patients in this study, according to the following titration schedule:

The contents of one 100 mg capsule will be dissolved in 10 ml water and then 5 ml of this solution (50 mg, dissolved in 5 ml water), will be administered once daily in the evening for two weeks.

If the 50 mg once daily dose is well tolerated (i.e., patient does not show signs of gastrointestinal side effects of diarrhea, reflux or gastrointestinal cramping), then the dose will be increased to 100 mg once daily for two weeks.

The 100 mg dose will be prepared by dissolving contents of one 100 mg capsule in 10 ml of water, followed by administration of the 100 mg dose (dissolved in the 10 ml water) once daily in the evening for two weeks.

If the 100 mg once daily dose is well tolerated (i.e., patient does not show signs of gastrointestinal side effects of diarrhea, reflux or gastrointestinal cramping), then the dose will

be increased to 100 mg twice daily for two weeks. Each 100 mg dose will be prepared by mixing contents of one 100 mg capsule in 10 ml of water for each dose, and using each dose immediately after preparation (do not save any unused portion of the mixture).

If the 100 mg twice daily dose is well tolerated (i.e., patient does not show signs of gastrointestinal side effects of diarrhea, reflux or gastrointestinal cramping), then the dose will be increased to 100 mg three times daily for two weeks. Each 100 mg dose will be prepared by mixing contents of one 100 mg capsule in 10 ml of water for each dose, and using each dose immediately after preparation (do not save any unused portion of the mixture).

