If the dose of 100 mg three times daily is well tolerated (i.e., patient does not show signs of gastrointestinal side effects of diarrhea, reflux or gastrointestinal cramping), then the dose will continue at 100 mg three times daily.

If the subject's BSA is $> 1.3 \text{ m}^2$, and if their insurance covers up to 600 mg/day miglustat, if the dose of 100 mg three times daily is well tolerated for two weeks, then increase dose to 100 mg in the morning and at midday and 200 mg in the evening for two weeks. If this dose is well tolerated, then increase dose to 200 mg in the morning, 100 mg at midday and 200 mg in the evening for two weeks. If this dose is well tolerated, then increase dose to 200 mg in the morning, 200 mg at midday and 200 mg in the evening for two weeks. If the dose of 200 mg three times daily is well tolerated (i.e., patient does not show signs of gastrointestinal side effects of diarrhea, reflux or gastrointestinal cramping), then the dose will continue at 200 mg three times daily.

If the subject's BSA is $> 1.3 \text{ m}^2$, but the subject's insurance does not cover miglustat dose of 200 mg three times daily, subject will use maximum dose of miglustat that is covered by the subject's insurance, not to exceed 600 mg/day miglustat.

10.13 Dose adjustment guidelines:

Peripheral neuropathy: If a patient is found to have peripheral neuropathy that is increased above pre-treatment levels, the dose of miglustat will be reduced by one-third and patient will be reassessed by neurologist 1 month later. If peripheral neuropathy has not resolved, the miglustat dose will be reduced by another one-third and the patient evaluated again after 1 month. If peripheral neuropathy continues, at the discretion of the neurologist, miglustat may be stopped.

Thrombocytopenia: If a patient is found to have thrombocytopenia, the dosing of miglustat will be held and CBC with platelets and differential checked weekly until platelet count recovers. If platelet counts do not recover after 2 weeks, then at discretion of study physician, miglustat therapy may be stopped, if deemed necessary under clinical discretion of study physician.

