21.0 Study Discontinuation

21.1 Discontinuation rules. The NIH and the University of Minnesota IRB have the authority to stop or suspend this study at any time. Additionally, the following study discontinuation rules apply:

- 1) That the rate of severe adverse events is such that continued participation would compromise subject safety.
- 2) Target subject accrual has not met, and cannot meet trial objectives.

21.2 Participant discontinuation. All data acquired prior to termination for the reasons outlined below will be included in the primary analysis unless patient withdraws consent. Every effort will be made to conduct a final study visit with the participant, and participants will be followed clinically until, if applicable, all adverse events resolve. Participant discontinuation in this study will occur for the following reasons:

- Participants who develop kidney function problems while in this study will be withdrawn from this study.
- Females who are able to become pregnant, and who are sexually active, must use a highly effective birth-control method to prevent pregnancy while in this study. If a participant becomes pregnant while in this study, they will be withdrawn from this study.
- If a patient develops bleeding due to low platelets while in this study, treatment with miglustat will be stopped.
- If a patient develops severe diarrhea and/or weight loss that cannot be managed by changing the ketogenic diet formula or lowering the miglustat dose, the patient will be removed from the study.
- Withdrawal of consent
- Withdrawal by the participant
- Withdrawal of the participant by the Investigator(s) (If a subject experiences an adverse effect from the treatment medication, dose reduction adjustments will be made to the medication, or the subject will be withdrawn from the study, if indicated.)

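### Below about 0.67 m² the 300 mg/day miglustat goal goes beyond the small-child doses reported in 10.10, and no blood count, weight or neuropathy exam is required between baseline and Month 3

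*Combined protocol and SAP*

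**What the plan says.** **Dose.** Section 10.10 gives children under 0.73 m² a goal of 100 mg three times daily, or whatever lower dose they tolerate. Section 10.12 reaches it through 50, 100, 200 and 300 mg/day, two weeks at each level.

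**Support for the dose.** 10.10 relies mainly on a pharmacokinetic and tolerability study. Its six infantile patients had "ages ranging between 1 year and 5 years and BSAs ranging between 0.4 m² and 0.7 m²". Doses for children under 0.8 m² were "titrated to the maximum tolerated dose (up to 270 mg per day", and final doses were 360–450 mg/m² and 15–20.9 mg/kg/day. 10.10 attributes the dose reductions in that study mainly to gastrointestinal effects. It also lists a two-patient infantile study. Section 7.0 says that the dose there was "increased to 200 mg daily after 3 months (divided into 3 doses daily) and this resulted in diarrhea and weight loss", and that both effects resolved at 100 mg/day.

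**Gate.** Each step in 10.12 depends on gastrointestinal tolerance, for example "If the 100 mg twice daily dose is well tolerated (i.e., patient does not show signs of gastrointestinal side effects of diarrhea", with reflux and cramping as the other two signs.

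**Named risks.** Section 10.9 lists peripheral neuropathy, diarrhea, weight loss and thrombocytopenia. It states "There is limited human experience in the use of miglustat in children (especially those less than 4 years of age", and separately "Overdoses in adults lead to neutropenia, which predisposes to severe infection".

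**Checks.** Sections 11.5 and 15.1 require weight, CBC with platelets and differential, and a neuropathy exam at baseline and then three-monthly in the first year. The matching row in section 17 is blank from Week 1 to Month 1.

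**Response rules.** Section 10.13: "If a patient is found to have thrombocytopenia, the dosing of miglustat will be held". Section 21.2: "If a patient develops bleeding due to low platelets while in this study, treatment with miglustat will be stopped".

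**The concern.** For the two larger BSA bands, 10.10 justifies the goal by matching the dose used in the supporting study. For the smallest band the goal is above what that study reports. A flat milligram dose gives the highest exposure per m² to the smallest children, and enrolment starts at age 0 (13.7).

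The gate for each step addresses the toxicity that limited dosing in that study, but not platelets, neutrophils, nerves or weight as such. The ketogenic diet comes first and is expected to lessen the gastrointestinal effects. If it does, more small children may pass the gate and reach 300 mg/day than would have without it.

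The platelet rule in 10.13 could act before any bleeding, but only on a count. None is scheduled until Month 3. What is at stake is early detection of an asymptomatic laboratory or neurological change in the youngest children. The survival analysis is not in question.

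**Working it through.** **Inputs.** Goal 3 × 100 = 300 mg/day (10.10). Supporting study: 50–90 mg three times daily, final doses 360–450 mg/m² and 15–20.9 mg/kg/day (10.10). Titration steps of 14 days (10.12). At least 2 weeks of stability on the diet before miglustat (10.11). Safety sets at baseline and Month 3, then Month 6 (11.5, section 17). Assumed: Month 3 = day 91, Month 6 = day 182.

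**The plan's own figures.** 3 × 90 = 270 mg/day, as stated. Four steps × 2 weeks = 8 weeks, as stated.

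**Time unit.** The mg/m² range carries none. Per day fits the reported doses: 150/0.4 = 375 and 270/0.6 = 450. Per single dose does not: even 90/0.4 = 225 falls short of 360.

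**Where 300 mg/day leaves the reported range.** By surface area, 300/450 = 0.667 m². By weight, 300/20.9 = 14.4 kg.

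| BSA (m²) | 300 mg/day in mg/m² | Ratio to 450 | 450 mg/m² in mg/day |
|---|---|---|---|
| 0.4 | 750 | 1.67 | 180 |
| 0.5 | 600 | 1.33 | 225 |
| 0.6 | 500 | 1.11 | 270 |
| 0.7 | 429 | 0.95 | 315 |

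At 10 kg, 300 mg/day is 30 mg/kg, or 30/20.9 = 1.44 times the upper end. The 200 mg/day step already passes the range below 200/450 = 0.44 m².

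**Time at goal before a scheduled count.** If every step is tolerated, 300 mg/day starts on day 3 × 14 = 42 of miglustat.

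- Month 3 counted from miglustat: 91 − 42 = 49 days, 7 weeks.
- Month 3 counted from the start of the diet, with run-in R days before miglustat: 91 − (R + 42) = 49 − R. For assumed R = 14, 28 and 42 this is 35, 21 and 7 days, or 5, 3 and 1 weeks.
- For R above 49 days, Month 3 falls before goal and the next set is Month 6. At R = 56, for example, the wait at goal is 182 − 98 = 84 days, although a Month 3 set would have been taken at a lower dose.

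The schedule does not say which clock applies.

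**What fills the interval.** Section 17 requires at least weekly calls during diet transition and titration. It also schedules evaluation by the diet team, including a neurologist, at baseline, Weeks 1–3 and Month 1. Sections 19.1 and 21.2 allow dose reduction or withdrawal for an adverse effect. None of these requires a blood count.

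**The case against.** The case against is substantial.

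- **The range is not a toxicity limit.** The final doses of 360–450 mg/m² were set by gastrointestinal tolerance. Nothing in the documents says that thrombocytopenia or neuropathy rises with mg/m² in children, or appears within weeks. The neutropenia statement concerns adult overdose, with no dose given. This stands: 450 mg/m² marks only where the reported experience ends.
- **The gate follows the dose-limiting toxicity reported.** In the two-patient study weight loss came together with diarrhea, and diarrhea stops escalation under 10.12. The plan also has a reason for going above 270 mg/day. Section 7.0 says diarrhea in the supporting study could be controlled by diet, and 19.3 expects a low-carbohydrate diet to help. This stands for gastrointestinal effects.
- **Supervision is closer than the laboratory row suggests.** Besides the calls and diet-team evaluations, 21.2 removes a child for severe diarrhea or weight loss that cannot be managed, and 19.1 sends adverse event reports to a medical monitor, generally monthly. Diet-team laboratory tests may be ordered when clinically indicated (20.4). So no test is required, but it would be wrong to say that none is done.
- **The site has experience at this dose.** Section 24.3 describes patients on the goal dose and the diet. It gives no BSA and no blood counts, so it softens the point without settling it.
- **The threshold depends on the metric.** Assuming BSA = √(height in cm × weight in kg / 3600), a child of 0.667 m² and 100–110 cm weighs 16.0–14.5 kg. Then 300 mg/day is about 18.7–20.6 mg/kg, inside the reported range. The excess is clear at 0.4–0.5 m² and marginal near 0.67 m².

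A reader might infer that the goal is an overdose for small children, or that 10.10 contradicts its own evidence. The documents support neither. The dose is titrated, may stop lower, and follows a diet meant to improve tolerance. It is an extrapolation.

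**Conclusion.** The point holds as a low-level safety improvement. Below about 0.67 m² the goal exceeds the final doses reported in 10.10, by 11% at 0.6 m² and 67% at 0.4 m². The steps to it are gated on gastrointestinal signs only. Because no CBC is required between baseline and Month 3, the 10.13 platelet rule may have nothing to act on for about 7 weeks at goal if Month 3 counts from miglustat. The wait is 5, 3 or 1 weeks if it counts from the diet with a run-in of 2, 4 or 6 weeks.

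This rests on reading 360–450 mg/m² as per day, on Month 3 at day 91, and on every step being tolerated on time. The run-in lengths are assumptions beyond the 2-week minimum. The number of affected children is unknown, because no BSA distribution is given.

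It would go too far to conclude that children are harmed, that they are unmonitored during titration, or that the survival result is affected. The documents show none of these.

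**What to change.** In 10.12 and section 17, for children under 0.67 m² who are newly starting miglustat:

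- Time the Month 3 safety set (weight, CBC with platelets and differential, neuropathy exam) at the end of the first two weeks at 100 mg three times daily, or at the highest dose reached if lower, before that dose is continued.
- Apply 10.13 to the result. It gives no numeric platelet threshold and no rule for neutrophils or weight, so those stay with the study physician.
- Resume the schedule at Month 6. The goal dose is unchanged.

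State which clock Month 3 uses. Time at goal before a count becomes 56 − 42 = 14 days. If the clock runs from the diet and the run-in exceeds 5 weeks (R + 56 > 91), the re-timed set would fall after Month 3. In that case keep Month 3 and add the new set.

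Optional: a weight and CBC before the step from 200 to 300 mg/day and, below 0.44 m², also before the step from 100 to 200 mg/day. This covers the smallest children, who otherwise spend days 28 to 56 above the reported range without a test.

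**Cost.** A short paragraph and one schedule entry. No new kind of procedure is added, and 11.5 allows these checks away from the primary site. Moving the set lengthens the interval to Month 6: on the miglustat clock from 13 to (182 − 56)/7 = 18 weeks, and on the diet clock with a 4-week run-in to (182 − 84)/7 = 14 weeks. Keeping Month 3 as well avoids this at the price of one extra blood draw. The optional checks add one or two more.

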Gastrointestinal side effects of miglustat: If a patient is having gastrointestinal side effects of nausea, vomiting, reflux, cramping, or diarrhea, the study doctors and ketogenic diet team will evaluate if there is a miglustat-carbohydrate interaction occurring that may involve too many carbohydrates in the diet, requiring dietary adjustments; and/or whether there are medications that patient may be taking that contain high levels of carbohydrate (i.e., liquid solution formulation of anti-seizure medications that are manufactured using simple syrup formulations). Medications made with high carbohydrate components such as simple syrups will need to be changed to unsweetened liquids or changed to a tablet or capsule form that may be crushed and administered via feeding tube. The study doctor will work with the patient's ketogenic diet

team to make these changes. If no dietary or medication cause of gastrointestinal side effects is found, miglustat should be stopped to see if symptoms resolve. If symptoms resolve after stopping miglustat, miglustat may be re-started at 50 mg once daily, and, if tolerated with no gastrointestinal side effects, the dose may be slowly titrated as tolerated, to goal dose or maximum dose tolerated, not to exceed goal dose for patient's BSA.

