20.0 Anticipated Risks

20.1 Anticipated risks of miglustat.²³ Potential risks to subjects include the following adverse drug events:

In clinical trials of miglustat in children with gangliosidoses, miglustat demonstrated an acceptable safety profile for use in young children. The most common side effects reported were diarrhea and weight loss. These gastrointestinal side effects of miglustat may be prevented or ameliorated by using a low-carbohydrate diet.

In clinical trials of adult patients with Gaucher disease type I, commonly reported side effects of miglustat included:

- Diarrhea (up to 100% of patients of patients with adult Gaucher disease type I)
- Flatulence (29-50% of patients of patients with adult Gaucher disease type I)
- Weight loss (39-67% of patients of patients with adult Gaucher disease type I)
- Abdominal pain (18-67% of patients of patients with adult Gaucher disease type I)
- Tremor (11-30% of patients with adult Gaucher disease type I)

20.2 Miglustat risk mitigation. Risks of gastrointestinal side effects may be mitigated by implementation of a ketogenic diet that may minimize or reduce the severity of food-drug interactions between carbohydrates and miglustat.

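### The 10.12 escalation rule omits nausea, vomiting and weight loss, nothing says whether it or 10.13 governs, and no weight is scheduled between baseline and Month 3

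*Combined protocol and SAP*

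**What the plan says.** **Escalation (10.12).** Miglustat starts at 50 mg/day and rises in two-week steps to 100, 200 and 300 mg/day. Each increase depends on the dose being *well tolerated*, which the section defines with an i.e. list: the "patient does not show signs of gastrointestinal side effects of diarrhea, reflux or gastrointestinal cramping". If that is met, the text directs the increase. For BSA above 1.3 m² with insurance cover, three further steps lead to 600 mg/day. The first reads "if the dose of 100 mg three times daily is well tolerated for two weeks, then increase dose to 100 mg in the morning" and repeats no list.

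**Gastrointestinal adjustment (10.13).** The trigger is wider: "If a patient is having gastrointestinal side effects of nausea, vomiting, reflux, cramping, or diarrhea". It leads to a review of diet and other medicines. If no cause is found, miglustat is stopped, with a possible restart at 50 mg once daily. After a restart, "if tolerated with no gastrointestinal side effects, the dose may be slowly titrated as tolerated".

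**Weight loss as a risk.** Section 20.1, on children with gangliosidoses, says: "The most common side effects reported were diarrhea and weight loss". Section 10.9 speaks of "known risks of peripheral neuropathy, diarrhea and weight loss". In the two-infant study described in 7.0, the dose was "increased to 200 mg daily after 3 months (divided into 3 doses daily) and this resulted in diarrhea and weight loss".

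**When weight is measured.** Sections 11.5 and 15.1 and the table in 17.0 schedule weight at baseline and every 3 months in the first year. The table row has no mark at Weeks 1 to 3 or Month 1. Section 10.11 requires "showing stability on the ketogenic diet for 2 weeks before starting miglustat therapy", but no weight is set for the end of those two weeks.

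**The concern.** The rule for going up and the rule for reacting to harm use different signs, and no sentence in the text available says which prevails or that escalation waits while a 10.13 review is under way. A child who vomits without diarrhoea, reflux or cramping passes the 10.12 test and triggers 10.13 at the same time.

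The weight gap is of another kind. A child who loses weight with none of the listed signs passes 10.12, and 10.13 has no weight criterion either. The children concerned are small and neurologically impaired, and they have just changed to a diet that may itself alter weight. Section 10.10 limits the dose to the maximum tolerated, but 10.12 is where tolerance is defined, so whatever is left out there is left out of that limit as well.

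What is at stake is safety during titration. The primary survival analysis is not affected.

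**Working it through.** **1. The signs side by side.**

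| Sign | 10.12 escalation | 10.13 trigger | 10.13 restart |
|---|---|---|---|
| Diarrhoea | yes | yes | yes |
| Reflux | yes | yes | yes |
| Cramping | yes | yes | yes |
| Nausea | no | yes | yes (any GI effect) |
| Vomiting | no | yes | yes (any GI effect) |
| Weight loss | no | no | not named |

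The 10.12 list is a strict subset of the 10.13 list. The missing items are nausea and vomiting.

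**2. The plan's own titration length.** Four dose levels (50, 100, 200, 300 mg/day) × 2 weeks = 8 weeks, which agrees with the roughly 8 weeks stated in 10.12. Counted from first dose, the increases fall at weeks 2, 4 and 6.

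**3. Position of the Month 3 weight.** Month 3 is 365.25 / 4 / 7 = 13.04 weeks, taken as week 13. Let L be the weeks from baseline to first miglustat dose. The increase to 300 mg/day falls at week L + 6, which is before week 13 when L < 7.

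The documents do not fix L. They give 2 stable weeks on the diet (10.11), a 2-3 day admission and an untimed move to 3:1 and 4:1 after discharge (11.4). Assuming a transition of t = 1 to 4 weeks, L = t + 2 = 3 to 6.

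| Dose reached (mg/day) | L = 0 | L = 3 | L = 6 |
|---|---|---|---|
| 100 | wk 2 | wk 5 | wk 8 |
| 200 | wk 4 | wk 7 | wk 10 |
| 300 | wk 6 | wk 9 | wk 12 |
| 400 (BSA > 1.3 m²) | wk 8 | wk 11 | wk 14 |
| 500 | wk 10 | wk 13 | wk 16 |
| 600 | wk 12 | wk 15 | wk 18 |

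- Time at 300 mg/day before the Month 3 weight: 13 − 6 = 7 weeks at L = 0; 13 − 9 = 4 weeks at L = 3; 13 − 12 = 1 week at L = 6.
- Time from reaching 200 mg/day to that weight: 9 weeks at L = 0; 6 at L = 3; 3 at L = 6.
- BSA above 1.3 m²: all six increases precede week 13 only if L + 12 < 13, that is L < 1. At L = 3, four of six do; at L = 6, three of six.
- At t = 5, L = 7 and the 300 mg/day step falls at week 13, level with Month 3. A held step has the same effect.

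**4. Scheduled contact between Week 4 and Month 3.** The table puts tolerance and diet-team reviews at Weeks 1 to 4 and next at Month 3. Of the three increases to 300 mg/day, one (week 6) falls between these at L = 0, and all three do at L = 3 to 6. In that interval the table provides the weekly titration call, which names no weight.

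**The case against.** The strongest reply is that the protocol already protects these children. The gastrointestinal paragraph of 10.13 has no time limit, so vomiting during titration calls for evaluation and possibly a stop. Section 10.10 sets the dose at the goal or the maximum tolerated, 19.1 provides dose reduction for adverse effects, and 21.2 names weight loss. Families are called at least weekly, and diet teams follow an institutional protocol, not among the documents, that may require weights. All of this stands. A reader might infer that the protocol obliges escalation in a child who is vomiting or losing weight, or has no answer to vomiting. The documents do not support that: what is missing is a statement of precedence and any link between weight and the decision to increase.

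A reader might also infer that every child reaches 300 mg/day before Month 3, or does so without ever having been weighed. Neither follows. The first depends on nominal titration and on L below about 7 weeks. The second overlooks the baseline weight. That weight may even fall close to first dose, because the table starts miglustat tolerance reviews at Week 1; in that case it is a usable reference, but the wait to Month 3 is then at its longest.

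Two side points carry little weight. A wider test at restart is reasonable in a child whose symptoms have already led to a stop. The list would naturally be read into the steps for BSA above 1.3 m², since it appears just before them and again at the end of the same paragraph.

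Finally, no child who would slip through is shown. In the two-infant study the weight loss came with diarrhoea, which 10.12 catches. In the 11-child study in 7.0, children with BSA below 0.8 m² took 50-90 mg three times daily (150-270 mg/day), and the drug was described as safe and tolerable, with mild to moderate diarrhoea controllable by diet. That limits the size of the concern; it does not supply the missing criterion.

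**Conclusion.** The point holds as a gap in the written escalation rule. Section 10.12 is narrower than 10.13 by nausea and vomiting, with no stated precedence, and it ignores a side effect that the protocol itself ranks among the most common in these children. No weight is scheduled between baseline and Month 3. All three increases to 300 mg/day fall inside that gap if titration runs to schedule and first dose comes less than about 7 weeks after baseline. The existing controls reduce the risk, but none ties weight to the decision to increase.

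At most 30 children are titrated (13.3). Those already on miglustat or the full regimen at enrolment (13.6, 17.0) may not be, and their number is not given. How many would vomit or lose weight without a sign listed in 10.12 cannot be told from the documents. This is a worthwhile, low-cost safety improvement.

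**What to change.** In 10.12, at every step including those for BSA above 1.3 m², define *well tolerated* as both:

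- none of the signs listed in 10.13, with nausea judged by observable behaviour such as retching or gagging; and
- no weight loss beyond a percentage set by the clinical team and written into the section, measured from a weight taken after the 2 stable diet weeks, just before the first miglustat dose.

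State that 10.13 overrides 10.12 and that escalation is held during a 10.13 review. Record a home or local weight, on the same scale each time, at the existing weekly call before each increase. If none can be obtained, the study physician decides and records why, so that titration does not stall.

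The limit should exceed scale error. As an illustration only: for an assumed 10 kg child and a scale accurate to ±0.1 to ±0.2 kg, two weighings can differ by 2 × 0.1 = 0.2 kg to 2 × 0.2 = 0.4 kg, or 2% to 4%, so a limit near 5% would clear it. That is not a clinical threshold.

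The cost is a wording amendment and one weight field in the call record: 1 + 3 = 4 weights to reach 300 mg/day, or 1 + 6 = 7 to reach 600 mg/day. No study-site visit or blood sample is added. The downside is that some children will reach goal dose later, and home weights are imprecise.
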